7. RESEARCH QUESTION AND OBJECTIVES

What is the real-world effectiveness of BNT162b2 formulations?

This study is descriptive in nature and as such does not include any pre-specified hypotheses.

Primary objective:

 To evaluate the VE of BNT162b2 formulations in non-pregnant, non-immunocompromised adults against medically attended COVID-19, mortality and healthcare resource utilization by age and adapted vaccine formulation.

Main summary measure: VE = (1 - adjusted hazard ratio [aHR]) * 100, comparing vaccinated to unvaccinated persons

Secondary objectives

 To assess VE of BNT162b2 formulations in pediatrics against medically attended COVID-19, non-COVID-19 respiratory infections, mortality and healthcare resource utilization by age and adapted vaccine formulation.

Main summary measure: VE = (1 - aHR) * 100, comparing vaccinated to unvaccinated persons

To estimate short-term (3A) and long-term (3B) healthcare resource utilization and costs associated with COVID-19 by vaccination status, age, and site of care.

Main summary measure: Inpatient healthcare expenditure comparing vaccinated to unvaccinated persons (3A), and total healthcare expenditure comparing COVID-19 to non-COVID-19 patients (3B).

Exploratory objectives

 To measure VE of BNT162b2 formulations in non-pregnant immunocompromised adults against medically attended COVID-19, mortality and healthcare resource utilization by age and adapted vaccine formulation.

Main summary measure: VE = (1 - aHR) * 100, comparing vaccinated to unvaccinated persons

 To quantify differences in VE of BNT162b2 formulations in non-pregnant, nonimmunocompromised adults when co-administered with seasonal influenza vaccines versus when each vaccine is given separately, by age groups.

> Main summary measure: aRR to evaluate non-inferiority, comparing people with coadministered vaccines to BNT162b2 vaccine alone for COVID-19-related outcomes

> Main summary measure: aRR to evaluate non-inferiority, comparing people with coadministered vaccines to seasonal influenza vaccine alone for influenza-related outcomes

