 - a. Or, have a location other than California or Louisiana in their HealthVerity claims enrollment file record but have one or more records in the California or Louisiana Immunization Registry. Examples include people who previously lived in Texas but moved to California/Louisiana and received a vaccine, or residents of other states who crossed state lines to receive a vaccine in California or Louisiana.

Matched Control Patients:

- 1. Control patients will be exact-matched up to 4:1 to COVID-19 patients using the following matching criteria:
 - a. Control patients will be assigned a random date between 01 June 2022 and 30 November 2022 as the index date. The control patients' index date will be further required to be within the \pm 14 days of the index date of their corresponding matched COVID-19 patients.
 - i. Have continuous medical and prescription insurance coverage between June 1, 2022 and November 30, 2022
 - ii. To ensure that the follow-up period of control patients will not be post-COVID-19, control patients are required to have no COVID-19 diagnoses in any position in any inpatient or outpatient claims prior to 30 November 2022.

- Control patients are allowed to have a COVID-19 diagnosis after 30 November 2022 as long as all other patient matching criteria are met. In such cases, the follow-up period of these control patients will be censored at the date of the first inpatient or outpatient claim with a COVID-19 diagnosis in any position.
- iii. Control patients will have similar continuous insurance enrollment criteria as the COVID-19 patients, described as below:
 - Similar to their matched adult and pediatric COVID-19
 patient counterparts, control patients will be required to have
 12 and 6 months of continuous baseline enrollment,
 respectively.
 - Control patients will be required to have continuous medical and prescription insurance coverage for at least 1 month after the index date (follow-up period).
- Control patients will be matched 4:1 without replacement to COVID-19 patients using the following criteria (exact match unless otherwise specified).
 - i. Index date within ± 14 days of the index date of the COVID-19 patient
 - ii. Age
 - Sample size permitting, an exact match of age will be used.
 If not, matched patients will be required to be within the same age group (see Table 1) AND have an age gap of no more than 2 years (control patient age = COVID-19 patient age ± 2 years).
 - iii. Gender
 - iv. State

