Total Costs of All Healthcare Claims - Baseline	Patient characteristic	HealthVerity	Sum of the costs of all healthcare, including inpatient, outpatient and pharmacy claims during the baseline period. Reported as min, max, median (Q1-Q3) and mean (SD).

Table 2. Follow-up Variables

Variable	Role	Data source	Operational definition
COVID-19 Hospitalization Status Within 30 Days (Yes/No)	Follow-up	HealthVerity	Whether patients had any inpatient COVID-19 hospitalizations within the 30-day period after the index date. Categories of Yes/No reported as counts and percentages.
Follow-up Duration	Follow-up	HealthVerity	Duration of the follow-up period (months). Reported as min, max, median (Q1-Q3) and mean (SD).
All-cause Hospitalization - Follow-up (Yes/No)	Outcome	HealthVerity	Proportions of patients with all-cause hospitalizations during the follow-up period. Reported as counts and percentages.
Number of All-cause Hospitalizations - Follow-up	Outcome	HealthVerity	Number of hospitalizations for any cause during the follow-up period. Reported as min, max, median (Q1-Q3) and mean (SD).
Total LOS of All-cause Hospitalizations - Follow-up	Outcome	HealthVerity	Sum of the LOS of all hospitalizations during the follow-up period. Any overlapping inpatient days will only be counted once. Reported as min, max, median (Q1-Q3) and mean (SD).
Total Costs of All- cause Hospitalizations - Follow-up	Outcome	HealthVerity	Sum of the costs of all hospitalizations during the follow-up period. Reported as min, max, median (Q1-Q3) and mean (SD).
All-cause Outpatient Visits - Follow-up (Yes/No)	Outcome	HealthVerity	Proportions of patients with all-cause outpatient visits during the follow-up period. Reported as counts and percentages.
Number of All-cause Outpatient Visits - Follow-up	Outcome	HealthVerity	Number of outpatient visits during the follow-up period. Reported as min, max, median (Q1-Q3) and mean (SD). Same measurements will be reported for the following sub-groups: office visits, emergency department, urgent care claims, others.
Total Costs of All- cause Outpatient Visits - Follow-up	Outcome	HealthVerity	Sum of the costs of all outpatient visits during the follow-up period. Reported as min, max, median (Q1-Q3) and mean (SD). Same measurements will be reported for the following sub-groups: office visits, emergency department, urgent care claims, others.

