5.6. Data Analyses

Descriptive statistics will be utilized to summarize patient demographic and clinical characteristics in addition to the measured HCRU and cost outcomes. Counts and percentages will be reported for categorical variables. Continuous variables will be summarized using minimum, maximum, median (Q1-Q3) and mean (SD).

All cost measurements will be adjusted to 2024 USD using Consumer Price Index medical care component.

All study measurements will be compared between the COVID-19 and Control cohorts.

HCRU and Cost Outcomes at Different Time Periods:

For HCRU and cost outcomes, all measurements will be provided for the following time periods:

- Post-acute phase: 1-11 months (measured starting from 30 days after the index date)
 - 1 to <2 months (1 month post-acute period)
 - 1 to <4 months (3 month post-acute period)
 - 1 to <7 months (6 month post-acute period)
 - 1 to <10 months (9 month post-acute period)
 - 1 to <12 months (11 month post-acute period)

Within this study, 1 month is generally considered to be equivalent to 30 days, unless otherwise specified.

NOTE: HCRU and cost will not be measured during the acute phase of 0 to <1 month after the index date since this is not within the study scope.

Stratification Analysis:

Patients will be further stratified by the following variables:

Age group:

 Among the overall study population, patients will be stratified by their age at the index date as follows:

- Adult and Pediatric
 - Adult: Patients ≥ 18 years at the index date.
 - Pediatric: Patients 6 months to < 18 years at the index date.
- Detailed Age Groups
 - Adult: 18 29, 30 49, 50 64, 65 74, 75+ years
 - Pediatric: 0 < 2, 2 4, 5 11, 12 < 18 years.
- COVID-19 Vaccination Status:
 - BNT162b2 Bivalent mRNA Vaccine
 - No Vaccine
 - NOTE: Other Vaccines sub-group for vaccination status will not be used for this stratification analysis.
- Site of Care: COVID-19 Hospitalization Status Within 30 Days (Yes/No):
 - Yes
 - No
- ICU Admission (Yes/No) Within 30 Days:
 - Among the overall study population, patients will be stratified by status of ICU Admission (Yes/No) – Within 30 Days
- IMV Usage (Yes/No) Within 30 Days:
 - Among the overall study population, patients will be stratified by status of IMV usage (Yes/No) – Within 30 Days

Sensitivity Analysis:

Sensitivity analyses planned for the study will include:

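### Aim 3B's strata by COVID-19 hospitalization, ICU admission and ventilation within 30 days leave the hospitalized stratum with no usable controls and the ICU and ventilation strata with non-comparable ones

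*SAP*

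**What the plan says.** Protocol section 7 gives the main Aim 3B measure as "total healthcare expenditure comparing COVID-19 to non-COVID-19 patients (3B"), and the objective asks for results by vaccination status, age and site of care. Section 5.6 of the Aim 3B SAP states that every study measurement is compared between the COVID-19 and Control cohorts.

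The stratification list in 5.6 then includes "Site of Care: COVID-19 Hospitalization Status Within 30 Days (Yes/No"). Table 2 in section 5.3 defines that variable as "Whether patients had any inpatient COVID-19 hospitalizations within the 30-day period after the index date". For intensive care, 5.6 says that "patients will be stratified by status of ICU Admission (Yes/No") within 30 days, and IMV has a parallel bullet. The ICU and IMV bullets both say that the split is made in the whole study population.

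The matched-control rules (the list inside section 5.2.1.2) set three conditions:

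- Index date: "Control patients will be assigned a random date between 01 June 2022 and 30 November 2022 as the index date".
- Eligibility: "control patients are required to have no COVID-19 diagnoses in any position in any inpatient or outpatient claims prior to 30 November 2022".
- A control with a later diagnosis "will be censored at the date of the first inpatient or outpatient claim with a COVID-19 diagnosis in any position".

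The outcome window in 5.6 is "Post-acute phase: 1-11 months (measured starting from 30 days after the index date"). Matching uses index date, demographics, state, insurance and baseline comorbidity and utilization, and nothing after index. No sentence says which stratum a control belongs to.

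**The concern.** All three stratifiers are events after index. One of them, COVID-19 hospitalization, is barred to controls by the rules that define a control. The other two are open to controls, but only by a different route from the cases. If a programmer classifies each person by their own status, as the definitions read, the within-stratum comparison no longer sets a severe case against people who resembled that case at baseline.

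At stake are the severity-specific excess costs. For hospitalized cases there would be no estimate. For ICU and ventilated cases there would be an estimate, but of something else: the later cost of a critically ill COVID-19 patient against that of a person critically ill from another cause. The second is the more troublesome, because an empty control column is obvious in a table and a non-comparable one is not.

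**Working it through.** **The plan's own figure.** Aim 3B SAP 5.5 claims power above 0.99. Inputs from that section: 50,000 cases, 4 controls per case (200,000), non-zero cost shares of 50% and 40%, alpha 0.05 (taken as two-sided).

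- Pooled share = (25,000 + 80,000) / 250,000 = 0.42.
- SE = √[0.42 × 0.58 × (1/50,000 + 1/200,000)] = 0.002468.
- z = 0.10 / 0.002468 = 40.5, so power is effectively 1.

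The figure reproduces. It describes the unstratified comparison and says nothing about the strata.

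**COVID-19 hospitalization, Yes.** Let *d* be a control's index date (1 June to 30 November 2022, 183 dates) and *h* the date of a COVID-19 admission. A Yes needs *d* ≤ *h* ≤ *d* + 30. Eligibility needs *h* on or after 30 November; a claim on that day is counted as allowed, which favours the plan. Together these require *d* ≥ 31 October.

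| Control index date | Number of dates | Can be Yes? | Post-acute days left |
|---|---|---|---|
| 1 June to 30 October | 152 (83%) | No | not applicable |
| 31 October to 30 November | 31 (17%) | Only by a claim on or after 30 November | 0 |

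In the second row the control is censored at or before *h*. Post-acute days = max(0, *h* − (*d* + 30)), which is 0 because *h* ≤ *d* + 30. Controls with usable outcome data: **0**, whatever the sample size.

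**Illustrative counts.** The documents give no hospitalized share, so 1%, 5% and 10% are assumptions. The 200,000 controls assume full 4:1 matching; the SAP says up to 4:1.

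| Share of cases hospitalized | Cases in Yes | Usable controls in Yes | Their matched controls, now in No | As % of all controls | Controls per case in No |
|---|---|---|---|---|---|
| 1% | 500 | 0 | 2,000 | 1% | 200,000 / 49,500 = 4.04 |
| 5% | 2,500 | 0 | 10,000 | 5% | 200,000 / 47,500 = 4.21 |
| 10% | 5,000 | 0 | 20,000 | 10% | 200,000 / 45,000 = 4.44 |

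At 5%, the No stratum still holds 47,500 cases with their own 190,000 controls, plus 10,000 controls whose case is elsewhere.

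**ICU and IMV, Yes.** Table 2 does not tie either variable to COVID-19, so a control enters through any critical illness within 30 days of a randomly assigned date. A control who enters through COVID-19 is censored before outcomes start, as above. Expected ICU controls = 200,000 × rate × 30/365. The background rate is an assumption:

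- 1 per 1,000 person-years: 200,000 × 0.001 × 30/365 ≈ 16
- 2 per 1,000: ≈ 33
- 10 per 1,000: ≈ 164

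If 1% of cases reach ICU (also assumed), 500 cases would face these few dozen to about 160 unmatched controls, in place of the 500 × 4 = 2,000 matched to them.

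**Do the regressions repair this?** The covariates listed in 5.6 contain no hospitalization, ICU or IMV term and no interaction of severity with cohort. They give no severity-specific contrast.

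**The case against.** The best defence is that the hospitalization split was meant to describe cases only. The Site of Care bullet, unlike those for ICU and IMV, does not say that it covers the whole study population. Protocol 8.7.4 lists COVID-19-related hospitalization as an outcome for cases only. Nor does the stratification section itself repeat the cohort comparison. That reading is possible for hospitalization, and classification by own status is an inference from Table 2. But the SAP does not state the cases-only reading, it sits badly with the instruction to compare all measurements between cohorts, and it does not fit the ICU and IMV bullets.

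Three stronger conclusions may tempt a reader, and the documents support none of them.

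- *That the site-of-care objective has no comparator.* Protocol 8.7.4 uses the term for the setting of care (inpatient, outpatient and so on). Table 2 measures inpatient, outpatient and pharmacy costs in follow-up, and these are compared between cohorts. In that sense the objective keeps its matched comparator.
- *That matching is destroyed in every stratum.* The No strata keep most matched sets whole and are only diluted. The planned regressions also adjust for the main matching variables.
- *That ICU and IMV excess costs will come out near or below zero.* Other-cause critical illness plausibly carries high later costs, so bias toward zero is a reasonable expectation. The documents hold no figure that establishes it.

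It is also fair to say that Aim 3B is a secondary objective of a study declared descriptive, and that its main contrast uses none of these strata.

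**Conclusion.** The point holds for the three stratified analyses. The empty hospitalized Yes stratum follows from the SAP's own rules once people are classified by their own status, and needs no assumed rate. For ICU and IMV, the Yes strata do not estimate the excess cost of severe COVID-19, because their controls are defined by a different illness and are not matched to those cases; the size and direction of the distortion are not established. The No strata carry surplus controls of about 1% to 10% under the assumed severe shares, with no bias quantified.

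The overall Aim 3B comparison, its stated power and costs by setting stand. Severity: should-fix.

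**What to change.** Add to section 5.6 of the Aim 3B SAP: *Hospitalization, ICU and IMV strata are assigned by the COVID-19 patient's status within 30 days; matched controls are analysed in the stratum of their matched COVID-19 patient.* Report COVID-19 versus Control within those matched sets. If any of the splits is meant only to describe cases, say so there and show no control column.

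Both cohorts must already have about a month of coverage after index, so starting outcomes at day 30 still works. Matching is on baseline only, so severe cases may still differ from their controls in ways not measured; a line in the report should say so.

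The cost is one sentence and a merge on the matched-set identifier, which the clustered standard errors already need. No new data are required.

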8.5. Study Size

Since the current study utilizes retrospective deidentified data without ability to recruit to a target, sample size calculations are not applicable. Further, this is a descriptive study without *a priori* specified hypotheses.

Initial data feasibility work has revealed approximately 19 million persons in the state of California with claims available in HealthVerity, among which approximately 25% are pediatric and 75% adult. Among these, approximately 12 million have at least one year of continuous medical and pharmacy enrollment. By end of 2023, we expect to have finished contracting to add approximately 565,000 additional persons. The proportion of these additional persons who will have 1-year continuous enrollment, and therefore the sample size estimates below have taken the conservative approach to not yet include these people.

We have identified 63% of persons in the claims data have at least one COVID-19 vaccine, and 16% received at least one bivalent dose. The claims population we have is not a random sample of Californians and may differ from the state's population in systematic ways (e.g. the age distribution). While differences may exist, we have high confidence in our ability to represent vaccination status for the individuals in our claims population.

We expect to begin to see XBB doses in data delivered in November 2023. Assuming uptake similar to that seen with the BA.4/5 vaccine, and non-differential uptake by age groups, we could anticipate in California:

(25% of 12 million are pediatric)*(16% uptake)*(60% of doses were Pfizer-BioNTech)

~ 288,000 pediatric XBB doses in California

(75% of 12 million are adult)*(16% uptake)*(60% of doses were Pfizer-BioNTech)

~ 864,000 adult XBB doses in California

Additional doses will be observed in Louisiana. In order to maintain patient de-identification, outcomes, covariates and subgroups will have at least 10 people in each category for inclusion in outputs. Throughout the protocol, this is referred to as "If sample size allows".

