5.2.1.1. Aim 3B Adult Inclusion Criteria

- 1. Born in 2004 or earlier (as age 18 or older as of the index date, owing to the data providing year but not month or day of birth).
- 2. Has COVID-19 diagnosis (ICD-10-CM code U07.1) in any setting, any position between 01 June 2022 and 30 November 2022 (first eligible code is the index date).
- 3. At least one year of continuous pharmacy and medical enrollment in HealthVerity prior to index date (ie, COVID-19 diagnosis). A gap of up to 30 days will be allowed.
- 4. Have been a State of California/Louisiana resident for at least one year prior to index date (ie, COVID-19 diagnosis)
- 5. Have continuous medical and prescription insurance coverage for at least 30 days after the index date (follow-up period).
 - The duration of the follow-up period will be required to be at least 1 month.
 - NOTE: since the evaluation of the long-term HCRU and cost starts from 1 month after the index date, this requirement for patients to have at least one month of follow-up is needed for this study.

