5.2.3. Follow-up

Patients will be followed for between 1 and 12 months after the index date. Patients will be censored at the earliest of: 1) disenrollment from insurance coverage; 2) the date of the first claim with a pregnancy diagnosis in the follow-up; 3) the end of data availability on 30 November 2023 or 4) receipt of COVID vaccination. Control patients may be further censored at the date of the first claim with a COVID-19 diagnosis after 30 November 2022.

A sensitivity analysis will be carried out where COVID-19 patients may be further censored at the date of COVID-19 reinfection. This will be further described in the latter part of the study protocol.

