Variable Operational definition Role **Data** source codes, HCPCS, and CPT-4 procedure codes. Reported as counts and percentages. ICU Duration - Within Outcome **HealthVerity** Number of days of ICU stay during the first 30 days of the follow-up period. Reported as min, max, 30 Days median (Q1-Q3) and mean (SD). IMV (Yes/No) - Entire Outcome Proportions of patients with IMV (i.e., intubation and **HealthVerity** MV, extracorporeal membrane oxygenation Follow-up [ECMO]) usage during the follow-up period, among patients with any hospitalizations in the follow-up period. IMV will be identified by HCPCS and CPT-4 procedure codes. Reported as counts and percentages. IMV Usage Duration -Outcome **HealthVerity** Number of days of IMV usage during the follow-up Entire Follow-up period. Reported as min, max, median (Q1-Q3) and mean (SD). ICU Admission Outcome HealthVerity Proportions of patients with ICU admission during (Yes/No) - Entire inpatient admissions within the follow-up period, Follow-up among patients with any hospitalizations in the follow-up period. ICU admission will be identified by hospital revenue codes, HCPCS, and CPT-4 procedure codes. Reported as counts and percentages. ICU Duration- Entire Outcome HealthVerity Number of days of ICU stay during the follow-up Follow-up period. Reported as min, max, median (Q1-Q3) and mean (SD). Oxygen Outcome HealthVerity Proportions of patients with oxygen Supplementation supplementation during the follow-up period, (Yes/No) among patients with any hospitalizations in the follow-up period. Oxygen supplementation will be identified by HCPCS and CPT-4 procedure codes. Reported as counts and percentages. **HealthVerity** Number of days of oxygen supplementation during Oxygen Outcome Supplementation the follow-up period. Reported as min, max, median Duration (Q1-Q3) and mean (SD). Proportions of patients with antiviral COVID drug Antiviral COVID Drug Outcome **HealthVerity** Usage Within 30 Days use within the 30-day period after the index date. After the Index Date Reported as counts and percentages. (Yes/No) COVID-19 Reinfection HealthVerity Proportions of patients with COVID-19 reinfection Outcome during the follow-up period. The COVID-19 (Yes/No) - Follow-up reinfection is defined as another COVID-19 diagnosis at least 90 days after the previous COVID-19 diagnosis. Reported as counts and percentages. Time to COVID-19 HealthVerity Outcome Days from the index date to the first claim date of Reinfection - Follow-up COVID-19 reinfection during the follow-up period. Reported as min, max, median (Q1-Q3) and mean All-cause Mortality **HealthVerity** Proportions of patients with all-cause mortality Outcome (Yes/No) during the index hospitalization or the follow-up

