1. COVID-19 reinfection: In the sensitivity analysis, a COVID-19 patient's follow-up period may be further censored at the first COVID-19 reinfection date (if any). The COVID-19 reinfection is defined as another COVID-19 diagnosis at least 90 days of gap after the previous COVID-19 diagnosis. The study measurements among the overall patient population (without stratifications) will be reported for this sensitivity population.

2. **Open-source Cost:** A portion of patients will have claims data that is linked to open-source cost information. A sensitivity analysis of the overall study analysis (not including the stratification analyses) will be carried out among such linked patients. The open-source cost data will be used to represent the cost information in this sensitivity analysis.

Statistical Analysis:

Descriptive Statistics:

Descriptive statistics will be utilized to summarize patient demographic, clinical characteristics, and HCRU and cost outcomes. Counts and percentages will be reported for categorical variables. Continuous variables will be summarized using minimum, maximum, median (Q1-Q3) and mean (SD). The count and percentage of patients with missing data will be reported.

Comparison Statistics:

All study measurements will be compared between the COVID-19 and Control cohorts. Standardized mean differences (SMD) will be reported for all variables.

Regression Analysis:

Multivariable regression analysis will be used to evaluate the potential predictors of long-term HCRU and costs associated with COVID-19.

- 1. The dependent variables of such regression models will include: number of all-cause hospitalizations during the follow-up period, total cost (charge and allowed amount) of all-cause hospitalizations during the follow-up period, number of COVID-19 hospitalizations during the follow-up period, total cost (charge and allowed amount) of COVID-19 hospitalizations during the follow-up period, total cost (charge and allowed amount) of all healthcare claims during the follow-up period, and total cost (charge and allowed amount) of COVID-19-related healthcare claims during the follow-up period.

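### Aim 3B reports reinfection as a plain percentage, although it needs a 90-day gap and follow-up may stop at 30 days; read as a risk, the figure is too low by an amount the documents do not fix

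*SAP*

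**What the plan says.** The percentage comes from the Aim 3B SAP, section 5.3, Table 2. The row is a Yes/No outcome over the follow-up period: "reinfection is defined as another COVID-19 diagnosis at least 90 days after the previous COVID-19 diagnosis. Reported as counts and percentages". The next row summarises days from index to reinfection by minimum, maximum, median, quartiles, mean and SD. Section 5.6 uses the same definition in a sensitivity analysis that censors cases at reinfection: "The COVID-19 reinfection is defined as another COVID-19 diagnosis at least 90 days of gap after the previous COVID-19 diagnosis".

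For adults, section 5.2.1.1 sets the entry rule on follow-up: "The duration of the follow-up period will be required to be at least 1 month". Section 5.2.1.2 repeats it for children. Section 5.2.3 adds: "Patients will be followed for between 1 and 12 months after the index date", and "Patients will be censored at the earliest of: 1) disenrollment from insurance coverage; 2) the date of the first claim with a pregnancy diagnosis", followed by end of data on 30 November 2023 and COVID vaccination. Section 5.6 fixes the unit: "Within this study, 1 month is generally considered to be equivalent to 30 days".

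Neither section states a minimum follow-up, a denominator or a time-to-event estimate for reinfection. Elsewhere in Table 2, the Yes/No rows for invasive ventilation, ICU admission and oxygen do limit their denominators, to patients hospitalised during follow-up.

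**The concern.** By definition, no reinfection can be recorded before day 90 after index, yet a case may leave follow-up from day 30. A case censored between those days cannot be a Yes. Since the row has no restriction where its neighbours do, the natural reading is that such a case stays in the denominator as a No. Cases censored after day 90 are likewise scored No for the remaining, unobserved months.

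Both effects push the percentage below the reinfection risk. The extent may also differ between strata with different censoring. Vaccination ends follow-up, and the bivalent vaccine was authorised for adults on 31 August 2022, inside the June to November 2022 index window, so the vaccination-status strata could be affected unequally. The mean and median time to reinfection describe only observed reinfections, with a floor at 90 days and a tail cut by censoring.

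At stake is the interpretation of one descriptive outcome. It is not a primary result.

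**Working it through.** The documents state no reinfection percentage and no Aim 3B loss rate, so there is no figure to reproduce. The check asks how large the shortfall would be under loss rates borrowed from elsewhere in the documents.

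**Which censoring matters.** The last index date is 30 November 2022 and data end on 30 November 2023, 365 days later. End of data therefore cuts no case short of 12 months of 30 days (day 360). Early loss comes from disenrollment, pregnancy or vaccination; death is not on the censoring list.

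**Inputs, none of them an Aim 3B loss rate**
- 5% censored by the end of the study period: simulation assumption in section 5.5 of the Aim 1 and Aim 2 SAPs, where follow-up is six months.
- 16% with at least one bivalent dose: Protocol 8.5, used here as if it were an annual vaccination rate.
- 12 of 19 million: Protocol 8.5 says "approximately 12 million have at least one year of continuous medical and pharmacy enrollment", out of about 19 million Californians with claims. It is used here as if it were annual retention.
- True reinfection risk R over days 90 to 360: not in the documents; 5% and 10% are illustrative.

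**Formulas.** Days 0 to 30 are guaranteed by the entry rule. Let L be a constant daily loss hazard from day 30, and g = −ln(1 − R)/270 a constant reinfection hazard from day 90 to day 360. Then:
- lost between day 30 and day 90 = 1 − exp(−60L)
- reported percentage, all cases in the denominator = exp(−60L) × g/(g + L) × [1 − exp(−270(g + L))]
- relative shortfall = 1 − reported/R

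**Worked example, 5% per 180 days, R = 5%.** L = −ln(0.95)/180 = 0.000285 and g = −ln(0.95)/270 = 0.000190. Reported = 0.983 × 0.400 × 0.1203 = 4.73%, a relative shortfall of 5.4%.

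| Assumed loss | L per day | Lost days 30–90 | Still followed at day 360 | R = 5% reported as | R = 10% reported as | Relative shortfall |
|---|---|---|---|---|---|---|
| 5% per 180 days | 0.000285 | 1.7% | 91% | 4.73% | 9.47% | about 5% |
| The same plus 16% per year vaccinated | 0.000763 | 4.5% | 78% | 4.32% | 8.65% | about 14% |
| 12/19 as annual retention | 0.001259 | 7.3% | 66% | 3.94% | 7.88% | 21% |
| The same plus 16% per year vaccinated | 0.001737 | 9.9% | 56% | 3.60% | 7.22% | 28% |

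**Which part comes from the 30-versus-90-day mismatch.** Dividing the reported figure by exp(−60L) restricts the denominator to cases followed to day 90. For R = 5%, the four figures become 4.81%, 4.52%, 4.24% and 4.00%, so shortfalls of 3.7%, 9.5%, 15.1% and 20.0% remain. Most of the shortfall is therefore loss after day 90, and a denominator rule alone would not remove it.

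**What a shortfall of one quarter would require.** Against 12-month risk, about 40% of cases lost by day 360. Against a denominator of cases followed at least 90 days, 25% lost before day 90, which under a constant hazard means 79% lost by day 360.

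**The case against.** The strongest reply is that Table 2 promises only what was seen during follow-up. It claims no 12-month risk, and follow-up duration is reported in the same table. As a descriptive count the row is correct, which is why the raw figure should stay. But a percentage of patients under unequal follow-up will be read as a risk, and a summary of follow-up duration does not correct it.

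Second, no sentence says that a case with under 90 days is coded No. That is true; it is an inference from the unrestricted row. The SAP reports missing-data counts but does not say that these cases are missing. If another coding is meant, the row must say so.

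Third, the SAP plans inverse probability of censoring weights (section 5.6). These are optional and apply to the regression models, where reinfection is not a dependent variable.

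Fourth, the replacement has limits. It assumes censoring unrelated to reinfection, which vaccination censoring may strain, and death is dated only to the month. Both points stand as caveats.

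A reader might also infer more than the documents support:
- That the percentage is about a quarter too low. The 12 of 19 million is a cross-sectional count that also leaves out recent entrants, and adult cases are already selected for a year of prior enrollment. It is not a disenrollment rate.
- That the bias exceeds ten standard errors. With the 50,000 cases expected in section 5.5 and R = 5%, the standard error is about 0.09 points. The bias is then about 3 standard errors in the first row of the table and 7 in the second, so the multiple depends on the assumed loss.
- That the cost estimates or the reinfection sensitivity analysis are distorted. Costs are summed over the same observed follow-up, so a reinfection after censoring adds nothing to them. The sensitivity analysis acts only on observed reinfections.

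**Conclusion.** The point holds in modest form. As an estimate of reinfection risk, the Table 2 percentage is biased downward, and the time summary describes observed reinfections only. The direction follows from the definition and the follow-up rules, given an all-cases denominator and loss unrelated to reinfection.

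The size cannot be settled from the documents. Relative to 12-month risk it is about 5% under the only censoring rate the SAPs assume, and about 14% with 16% annual vaccination added. It reaches 21–28% only by treating an enrollment count as annual retention. These figures also assume constant hazards. Reinfection is a descriptive outcome in Aim 3B and the effect on the cost results is small, so this is an improvement to one table, not a threat to the aim.

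**What to change.** In Table 2 of the Aim 3B SAP:
- Report the number of cases with under 90 days of follow-up.
- Report the cumulative incidence of reinfection from day 90 among cases still in follow-up at day 90, at 6, 9 and 12 months with 95% CI. Use Kaplan-Meier, or Aalen-Johansen with death as a competing event on month-level death dates, with the section 5.2.3 censoring rules.
- Keep the raw count and percentage, labelled as observed during follow-up, with the denominator stated.
- Show the time-to-reinfection summary only beside the curve.

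The cost is SAP wording and one standard survival procedure on data already held. The downsides are one more curve to present, a coarse date for the competing event, and the independent-censoring assumption, which should be stated with vaccination named as the doubtful case.
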